9.4 Analysis Endpoints

Primary Endpoints

1. Safety: AEs, vital signs, electrocardiograms, clinical chemistry, hematology, urinalysis, targeted neurological exams, Columbia suicide severity rating scale.

Baseline is defined as the pre-dose measurement at Day 1.

Secondary Endpoints

1. Pharmacokinetics: the plasma PK parameters of MK-1942 after administration of MK-1942 + donepezil - C_{max}, T_{max}, C_{trough}, AUC₀₋₁₂, AUC₀₋₂₄ (days 21 and 28), and CL_{ss}/F (days 21 and 28), V_{zss}/F (days 21 and 28), apparent terminal t_{1/2} (Day last – 21 or 28 only).
2. Pharmacokinetics: the plasma PK parameters of donepezil after administration of donepezil alone and donepezil + MK-1942 (Days -1, 21, and 28) - C_{max}, T_{max}, and AUC₀₋₂₄.

Exploratory Endpoints:

1. MMSE-2 and DSST scores obtained at baseline (screening) and from the last day of dosing.
2. 12-lead ECG parameters

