^h Patients will take the first dose of MK-1942/placebo in the AM along with daily donepezil treatment. Patients will be dosed BID with MK-1942/placebo, except on Day 28, when only the morning dose is administered. If Dose Level 4 is not given, only the AM dose of Dose Level 3 will be given on Day 21.
ⁱ Patients will take their personal donepezil prescription QD in the AM. Those patients who do not take donepezil in the AM should be advised to start morning dosing on Day -7.
^j VS measures out of normal range will be repeated up to 3 times in 15 minutes, or until measures return to normal.
^k **Days 1, 7, 8, 14, 15, 21, 22, and 28 are intense monitoring days:** Single measures of semi-recumbent HR and BP to be taken predose (triplicate on Day 1), 2 and 4 hrs after the AM dose. Days -1, 2, 3, 4, 9, 10, 11, 16, 17, 18, 23, 24, and 25: Single measures of HR and BP to be taken predose and ~ 2 hrs after the AM dose. Days 29 and 30: HR and BP to be taken at ~ 24 and 48 hrs postdose relative to Day 28, respectively. Single measures of RR, BT taken predose on Day 1 and ~ 2 hrs after the AM dose on Days 1, 7, 8, 14, 15, 21, 22 and 28.
^l Days 1, 7, 8, 14, 15, 21, 22, and 28: Orthostatic HR and BP to be taken pre-dose on Day 1 and ~ 2 hrs after the AM dose. Days 29 and 30: orthostatic measures can be taken at ~ 24 and 48 hrs relative to post-dose Day 28.
^m All ECGs will be measured in triplicate. **Days 1, 7, 8, 14, 15, 21, 22, and 28 are intense monitoring days:** predose and ~ 1, 2, 3, 4, 6, 8, and 12 hours after the AM dose. Days 2, 3, 4, 9, 10, 11, 16, 17, 18, 23, 24, and 25: predose and ~ 2 hours after the AM dose. Days 29 and 30: ~ 24 and 48 hrs after the Day 28 dose.
ⁿ Days -1, 8, 15, 22, and 28: ~ 2 hrs after the AM dose of donepezil. Day 30: ~ 48 hrs after the Day 28 dose.
^o Days -1, 1: ~ 1.5 hours after AM dose of donepezil. Days 4, 7, 8, 11, 14, 15, 18, 21, 22, 25, and 28: ~ 1.5 hours after AM dose, or more frequently as required by investigator. Day 29: ~ 24 hrs after AM dose Day 28.
^p Day 1: before AM dose. Days 8, 15, 22, and 28: ~ 4 hrs after the AM dose. Day 30: ~ 48 hrs after the AM dose on Day 28.

Study Period	Screening		Intervention (Days) ^a																									Post-Treatment Safety Monitoring			Post-study						
Scheduled Day	Up to day -35	-2	-1	1	2	3	4	5	6	7	8	9	10	11	12	13	14	15	16	17	18	19	20	21	22	23	24	25	26	27	28	29	30	31	42		

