
^a Days 1, 7, 14, 21, and 28 are intense PK sampling days. Blood samples will be taken predose, and at 0.5, 1, 2, 3, 4, 6, and 12 hours post AM dose. On Day 28 (or last day of dosing), administer the AM dose only and sample predose, 0.5, 1, 2, 3, 4, 6, 12, 24, 48, and 72 hr post-dose. On Days 2, 4, 8, 9, 11, 15,16, 18, 22, 23, and 25 a sample will be taken before the AM dose (Ctrough).
 
^r Days -1 and 28 are intense PK sampling days. Samples to be taken pre-dose and 0.5, 1, 2, 3, 4, 6, 12 and 24 hrs post-dose. On Day -1 time points are relative to the morning donepezil dose. If Dose Level 4 is not given, Day 21 will be the second intense PK sampling day instead of Day 28.
 
^s Pre-dose from enrolled participants only – See Section 8.8.
																																					

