The plasma PK of MK-1942 following multiple dose co-administration with donepezil will be characterized by determining the C_{max}, T_{max}, C_{trough}, and AUC₀₋₁₂ after the first dose. In addition, C_{max}, T_{max}, C_{trough}, AUC₀₋₁₂, AUC₀₋₂₄, apparent terminal t_{1/2}, CL_{ss}/F, V_{zss}/F and accumulation ratio will be determined at steady state. This will allow doses and dosing regimens in elderly participants with AD to be identified that produce systemic exposures in the predicted efficacious range ^{CCI} [REDACTED] while providing insights into the ability of donepezil to alter the PK of MK-1942.

Similarly, the plasma PK of donepezil following once daily administration will be characterized by determining the C_{max}, T_{max}, and AUC₀₋₂₄ on the day before administration of the first dose of MK-1942 and after 21 (28) days of co-administration. Determining the C_{max} and AUC₀₋₂₄ of donepezil during co-administration with MK-1942 will provide insights into the ability of MK-1942 to alter the PK of donepezil.

Exploratory Endpoints

The Mini-Mental State Exam, edition 2 (MMSE-2) will be administered to AD patients at screening and upon completion of up to 28 days of treatment. The score from the MMSE-2 given at screening will be used as an inclusion criterion, to ensure that AD patients being enrolled fall into the cognitive impairment categories of mild to moderate severity. The MMSE-2 is a 30-point examination evaluating Registration, Orientation to Time, Orientation to Place, Attention, Recall, Language, Repetition, Complex Commands, and Recall tasks. A score between 21 to 26 typically indicates that a subject is experiencing mild cognitive impairment, while scores in the range of 10-20 are indicative of patients with moderate cognitive impairment. This study proposes to enroll individuals with mild to moderate cognitive impairment as indicated by scores between 17 to 26. This range will allow for broader recruitment while reducing the burden on CRU personnel associated with caring for patients with MMSE-2 scores < 17. In addition to its use as a screening tool for identifying

candidate participants as having mild to moderate cognitive impairment, the MMSE-2 will be used as an exploratory endpoint to determine whether the treatment regimen results in any changes from the initial score.

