8.1.8.1 Timing of Dose Administration

The first oral doses of MK-1942/placebo will be administered in the morning at approximately the same time every day. After all pre-dose procedures are completed on the morning of Day 1, either MK-1942 or placebo will be administered (Section 8.1.8), with the time of administration constituting Time "0". All capsules will be distributed and consumed within 10 minutes of the recorded administration time. Participants will remain resting in bed in a semi-recumbent position for approximately 2 hours after dosing. Participants may ambulate freely after the 2-hour VS and ECGs if no clinically significant changes are observed.

Participants will receive the second daily oral dose of MK-1942/placebo approximately 12 hours after the time the first daily dose was administered. All capsules will be administered within 10 minutes of the of the exact time when treatment is administered, and that administration time recorded. On Day 21 (28), only the morning dose will be administered. Participants will remain resting in bed in a semi-recumbent position for approximately 2 hours after dosing. Participants may ambulate freely after the 2-hour VS and ECG measures if no clinically significant changes are observed.

Donepezil will be administered in the mornings at approximately the same time as MK-1942/placebo. If participants do not usually take their Donepezil in the mornings, they should be instructed to start taking it in the morning starting on Day -7.

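### Does the morning-only last dosing day make the steady-state MK-1942 AUC0-24 unobtainable or understated?

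*Combined protocol and SAP*

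**What the plan says.** Section 9.4 names, for MK-1942, "AUC₀₋₂₄ (days 21 and 28), and CL_{ss}/F (days 21 and 28" among the secondary endpoints, alongside Cmax, Tmax, Ctrough and AUC0-12. In Section 4.2.1, under Pharmacokinetic Endpoints, "AUC₀₋₂₄, apparent terminal t_{1/2}, CL_{ss}/F, V_{zss}/F and accumulation ratio will be determined at steady state".

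The dosing text is consistent throughout. Section 1.3: "Patients will be dosed BID with MK-1942/placebo, except on Day 28, when only the morning dose is administered", and "If Dose Level 4 is not given, only the AM dose of Dose Level 3 will be given on Day 21". Section 8.1.8.1 agrees: "On Day 21 (28), only the morning dose will be administered".

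Sampling is set in the PK footnote of Section 1.3. On intense days, "Blood samples will be taken predose, and at 0.5, 1, 2, 3, 4, 6, and 12 hours post AM dose". On the last dosing day the instruction is to "administer the AM dose only and sample predose, 0.5, 1, 2, 3, 4, 6, 12, 24, 48, and 72 hr post-dose". Single pre-dose troughs are drawn on eleven other days, including Day 22.

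Section 9.6.2 models MK-1942 Cmax, AUC0-12 and Ctrough against the healthy elderly volunteers of MK-1942-004. MK-1942 AUC0-24 is not modelled; it falls under the listings and descriptive statistics. No section gives a formula for AUC0-24 or says which area CLss/F is based on.

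**The concern.** A steady-state AUC0-24 under twice-daily dosing should cover two doses. None of the days listed for it has both two doses and a sampled evening interval. On the last dosing day the second 12 hours are washout. On Day 21, when Dose Level 4 follows, the evening dose is given but the next sample is the Day 22 trough, so the evening peak goes unseen.

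If an analyst integrated the observed points from 0 to 24 h and reported the result as daily exposure, it would be too low, and it would mean different things on Day 21 and Day 28. Dividing the full daily dose by it would make CLss/F too high. Daily exposure could matter when observed values are set against the projections in Section 4.3.2 or the exposure limits in Section 6.6.1. Donepezil adds to the unease: its AUC0-24 has the same label but is validly integrated directly, because it is dosed once daily and sampled to 24 h.

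**Working it through.** **Is any evening sampling planned?** Inputs are the PK footnote of Section 1.3 and the blood-volume table in Appendix 8.

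- Days 1, 7, 14 and 21: 4 x 8 = 32 samples
- Day 28: 11 samples
- Troughs on Days 2, 4, 8, 9, 11, 15, 16, 18, 22, 23 and 25: 11 samples
- Total: 32 + 11 + 11 = 54; at 4 mL each, 216 mL

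Appendix 8 states 54 collections and 216 mL. The match is exact, so no sample after an evening dose is planned on a twice-daily day.

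**How low would direct integration be?** The half-life (t½) is redacted in Section 2.2.3.1, so 4 to 24 h is an assumption. With one compartment and dose D every 12 h at steady state, each interval has area D/CL, and a two-dose day has 2D/CL. If the evening dose is omitted, the second 12 hours contribute (D/CL) x 2^(-12/t½), ignoring absorption. So

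ratio = (1 + 2^(-12/t½)) / 2.

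For t½ = 6 h: (1 + 0.25)/2 = 0.63. For 12 h: (1 + 0.5)/2 = 0.75. For 24 h: (1 + 0.707)/2 = 0.85.

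The next table adds first-order absorption (assumed rate 1 per hour) and uses the linear trapezoid at the scheduled times. Each entry is a share of the true two-dose AUC0-24.

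| Assumed t½ (h) | Last day, morning dose only | Day 21, Dose Level 4 following (0-12 h plus Day 22 trough) | 2 x AUC0-12, same samples |
|---|---|---|---|
| 4 | 61% | 69% | 102% |
| 6 | 67% | 77% | 101% |
| 8 | 71% | 81% | 100% |
| 12 | 78% | 87% | 100% |
| 18 | 83% | 91% | 100% |
| 24 | 87% | 93% | 100% |

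With an absorption rate of 2 per hour, the two direct-integration columns fall by at most about 2 points and the last column is essentially unchanged.

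**What about CLss/F?** Single dose divided by AUC0-12 is unaffected. Only daily dose divided by the morning-only area would be inflated, by 1/ratio - 1: 1/0.625 - 1 = 60% at t½ 6 h and 1/0.854 - 1 = 17% at 24 h. The plan does not specify that calculation.

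**Is the correct value available?** Yes. At steady state AUC0-24 = 2 x AUC0-12, and 0-12 h is sampled on both listed days. Each dose level lasts 7 x 24 = 168 h, which is 7 half-lives even at the 24 h end of the assumed range, so steady state at the end of a level is a fair premise.

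**The case for a change.** The best argument for acting is that Section 9.4 leaves AUC0-12 open to all profile days but ties AUC0-24 to Days 21 and 28. If AUC0-24 simply meant 2 x AUC0-12, it could equally be given for Days 7 and 14. The restriction might therefore signal that the observed 24 h sample will be used, which is the calculation that comes out low. Section 4.2.1 also ties these parameters to finding regimens in the predicted efficacious range, and Section 6.6.1 limits escalation by exposure.

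The inference does not hold. CLss/F carries the same day restriction, although it needs only AUC0-12, which Days 7 and 14 also supply; the restriction therefore says nothing reliable about the method. Nor could a sampled two-dose AUC0-24 ever have been intended for Day 21 with Dose Level 4 following. The day list may itself be loose: the donepezil line of Section 9.4 names both Day 21 and Day 28, although Section 1.3 samples donepezil on Day 21 only in place of Day 28. The half-life entry, which spells out the last day, points the other way, so the wording is ambiguous.

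As for use, the projections in Table 6 are not visible and the metric behind the exposure limits is not stated. No visible text sets observed AUC0-24 against either.

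What stands is that the derivation is unwritten, and that a directly integrated area presented as two-dose daily exposure would be low at every half-life examined. It is also true that 2 x AUC0-12 treats the evening interval as equal to the morning one, while Section 5.3.1.1 has the morning dose follow a longer fast. That is an ordinary approximation for a descriptive parameter.

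**Conclusion.** No change is needed. The schedule is as described, but the endpoint is obtainable: the planned 0-12 h samples give the steady-state daily area to within 0-2% across the assumed half-lives. The understatement, about 13-39% on the last day and 7-31% on Day 21 with Dose Level 4 following, arises only if the area is integrated directly and then presented as a two-dose day. The CLss/F inflation needs the further step of dividing the daily dose by that area. The plan prescribes neither.

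This is missing detail of a kind that pharmacokineticists fill as routine; the plan gives no formula for Vzss/F or the half-life either. Nothing confirmatory depends on it: the hypothesis and the power statement concern Cmax, the other modelled MK-1942 comparisons use AUC0-12 and Ctrough, and donepezil AUC0-24 is correctly supported by once-daily dosing and sampling to 24 h. The percentages rest on an assumed half-life of 4-24 h, one-compartment linear kinetics and absorption rates of 1-2 per hour. The conclusion does not depend on where in that range the true half-life lies.

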9.5 Analysis Populations

The following populations are defined for the analysis and reporting of data. All participants will be reported, and their data analyzed, according to the treatment(s) they actually received.

All Subjects as Treated (ASasT): The All Subjects as Treated Population consists of all participants who received at least one dose of treatment. This population will be used for assessments of safety and tolerability.

Per-Protocol (PP): The Per-Protocol Population consists of the set of data generated by the subset of participants who comply with the protocol sufficiently to ensure that these data will be likely to exhibit the effects of treatment, according to the underlying scientific model.

Compliance covers such considerations as exposure to treatment, availability of measurements and absence of important protocol deviations. Important protocol deviations will be identified to the extent possible prior to unblinding by individuals responsible for data collection/compliance, and its analysis and interpretation. Any participants or data values excluded from analysis will be identified, along with their reason for exclusion, in the CSR. At the end of the study, all participants who are compliant with the study procedure as aforementioned and have available data from at least one dose level will be included in the Per-Protocol dataset. This population will be used for the PK analyses.

9.6 Statistical Methods

9.6.1 Safety

Summary statistics and plots will be generated for raw laboratory safety tests, ECGs, and/or vital signs as well as for change from baseline, as deemed clinically appropriate. Depending on the safety parameter, the difference from baseline will either be computed on the original scale (raw change from baseline) or on the log scale and back-transformed for reporting (percent change from baseline).

The frequency and severity of subjective reports of AEs over the dosing period will be closely monitored and reported. The counts and frequency of AEs will be summarized by treatment. In addition, posterior probabilities (PP) of the incidence of dizziness, nausea, emesis after co-administration of MK-1942 and donepezil to AD patients that are less than a target rate will be provided. Such analyses may also be provided for other AEs identified during the study. The target rate is determined from the incidence of an AE associated with MK-1942 alone from MK-1942 P004, and the maximum tolerable increase in the incidence of an AE. For example, if the true AE rate of MK-1942 alone is 40% and the maximum tolerable increase in AE incidence associated with MK-1942 + donepezil compared to MK-1942 alone is 20%, the target rate would be 60%. A posterior probability greater than 60% will be considered as tolerable.

Responses to the C-SSRS will be tabulated and the individual score > 0 will be listed. The difference from pre-treatment baseline values will also be determined.

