Hot flush	0	(0.0)	0	(0.0)	0	(0.0)	0	(0.0)	0	(0.0)
Hypertension	0	(0.0)	0	(0.0)	0	(0.0)	0	(0.0)	0	(0.0)
Orthostatic hypotension	0	(0.0)	0	(0.0)	0	(0.0)	0	(0.0)	0	(0.0)

**SUBJECTS WITH ADVERSE EVENTS
 (INCIDENCE > 0% IN ONE OR MORE TREATMENT GROUPS)**

	Panel E		Panel F		Placebo		Follow-Up	
	n	(%)	n	(%)	n	(%)	n	(%)
Vascular disorders	1	(12.5)	1	(12.5)	2	(25.0)	0	(0.0)
Haematoma	0	(0.0)	0	(0.0)	0	(0.0)	0	(0.0)
Hot flush	1	(12.5)	1	(12.5)	0	(0.0)	0	(0.0)
Hypertension	0	(0.0)	0	(0.0)	1	(12.5)	0	(0.0)
Orthostatic hypotension	0	(0.0)	0	(0.0)	1	(12.5)	0	(0.0)

Every subject is counted a single time for each applicable row and column.

A system organ class or specific adverse event appears on this report only if its incidence in one or more of the columns meets the incidence criterion in the report title, after rounding.

QD=once a day; BID=twice a day

Adverse event terms are from MedDRA Version 22.0

Source: [P002V01MK1942: adam-adsl; adae]

CCI

2.2.3.2 MK-1942-004: A Randomized, Double Blind, Placebo-Controlled Investigation of the Safety, Tolerability and Pharmacokinetics of Multiple-Dose Regimens of MK-1942 in Healthy Elderly Participants

MK-1942-004 is a study of the safety and PK of MK-1942 when administered as multiple dose regimens. The study consists of 3 panels, with Panels A and C each comprised of 8 healthy elderly participants of both genders and Panel B consisting of 8 healthy adults of both genders receiving either MK-1942 (N=6) or placebo (N=2). Participants will be enrolled in only one panel of the study. All participants are domiciled during the treatment period (Panel A: 21 days, Panels B and C: up to 28 days) and for 2 days after completion of dosing for safety monitoring ([Table 5](#)). The study will employ multiple dose and titration dosing regimens of varying dose levels (not to exceed 50-mg), dosing frequencies (not to exceed BID) and dosing durations (up to 28 days in total).

Table 5 Proposed Dosing Regimens for MK-1942-004-001

Panel	A			PK Break	B				PK Break	C			
Treatment	5-mg BID x 7D	10-mg BID x 7 D	20-mg BID x 7D	3 weeks	8-mg BID x 7D	15-mg BID x 7D	30-mg BID x 7D	50-mg BID x 7D	3 weeks	8-mg BID x 7D	15-mg BID x 7D	30-mg BID x 7D	50-mg BID x 7D

Abbreviations: BID= bis-in-diem (twice daily); D=day; PK= pharmacokinetics

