3 HYPOTHESES, OBJECTIVES, AND ENDPOINTS

Hypotheses are aligned with objectives in the Objectives and Endpoints table.

Details of the hypotheses to be tested can be found in Section 9.3.

Objectives	Endpoints
Primary	

Evaluate the safety and tolerability of treatment (MK-1942 co-administered with donepezil) in AD patients with mild-to-moderate cognitive impairment.	
Safety measures (VS, ECGs, clinical chemistry, hematology, urinalysis, targeted neurological exams, Columbia suicide severity rating scale) and Adverse Event reports
Secondary	

Evaluate the effects of donepezil on the PK of MK-1942 in AD patients 
Hypothesis
 
The plasma Cmax of MK-1942 determined on the last day of a titrated treatment regimen (Day 21 [28]) when co-administered with donepezil to AD patients is similar to the Cmax obtained following administration of MK-1942 to HEV from MK-1942-004, Panel C. That is, the true GMR (MK-1942 + donepezil in AD / MK-1942 in HEV) is contained within the interval (0.5, 2.0).	
Cmax, AUC0-12, AUC0-24, Ctrough, Tmax, apparent terminal t1/2, CLss/F, and Vzss/F of MK-1942AUC0-24, Cmax, Ctrough, Tmax for donepezil

Objectives	Endpoints

 Evaluate the effects of MK-1942 on the PK of donepezil in AD patients. Estimation: 
 The true GMRs of plasma PK parameters (AUC₀₋₂₄, C_{max}) for donepezil before and during administration of donepezil + MK-1942 to AD patients will be estimated. 	
Tertiary/Exploratory	

 Evaluate the changes in cognitive function of AD patients by comparing the MMSE-2 and DSST scores obtained at baseline with those from the last day of dosing. Explore the relationship between plasma concentrations of MK-1942 and corrected QT intervals. CCI [REDACTED] Explore the relationships between genetic variation, response to the treatment(s) administered, and mechanisms of disease. Variation across the human genome may be analyzed for association with clinical data collected in the study. 	
 MMSE-2 scores DSST scores QTcF Germline genetic variation

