9.1 Statistical Analysis Plan Summary

Safety

Summary statistics and plots will be generated for raw laboratory safety tests, ECGs, and/or vital signs as well as for change from baseline, as deemed clinically appropriate. Depending on the safety parameter, the difference from baseline will either be computed on the original scale (raw change from baseline) or on the log scale and back-transformed for reporting (percent change from baseline).

Frequency and severity of subjective reports of AEs over the dosing period will be closely monitored and reported. The counts and frequency of AEs will be summarized by treatment. In addition, posterior probabilities (PP) of the incidence of dizziness, nausea, emesis after co-administration of MK-1942 and donepezil to AD patients that are less than a target rate will be provided. Such analyses may also be provided for other AEs identified during the study. The target rate is determined from the incidence of an AE associated with MK-1942 alone from MK-1942 P004, and the maximum tolerable increase in the incidence of an AE. For example, if the true AE rate of MK-1942 alone is 40% and the maximum tolerable increase in AE incidence associated with MK-1942 + donepezil compared to MK-1942 alone is 20%, the target rate would be 60%. A posterior probability greater than 60% will be considered as tolerable.

Responses to the C-SSRS will be tabulated and the individual score > 0 will be listed. The difference from pre-treatment baseline values will also be determined.

Pharmacokinetics

Model-based PK Summary

Evaluation of the effects of donepezil on the PK of MK-1942 in AD patients

At each dose level, individual values of the plasma C_{max} of MK-1942 on the last day of a titrated treatment regimen after co-administration of MK-1942 with donepezil to AD patients, as well as the C_{max} of MK-1942 after administration of MK-1942 alone to HEV in MK-1942-004 will be natural log transformed and analyzed in an ANOVA model. The model contains one factor for treatment (MK-1942 alone in HEV, MK-1942+donepezil in AD patients).

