With 18 AD patients receiving MK-1942 + donepezil and a target rate of 80%, if the true AE rate following administration of MK-1942 + donepezil in AD patients is 60%, there is a probability of 97% that co-administration of MK-1942 with donepezil is considered safe and tolerable.

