9.9 Sample Size and Power Calculations

PK:

The estimated pooled, between-subject standard deviations on log scale for MK-1942 Cmax on the last day of dosing following administration of ^{CCI} [REDACTED] BID doses of MK-1942 for 5 to 10 days in healthy subjects in MK-1942-002 is 0.225. Assuming the standard deviation is 30% higher in AD patients than HEV, i.e. the between-subject standard deviation on a log scale for Cmax is 0.29 in AD patients, if the true GMR (MK-1942+donepezil in AD patients/MK-1942 alone in HEV) is 1.00, with 18 AD patients receiving MK-1942 and donepezil and 6 HEV receiving MK-1942 alone in MK-1942-004, there is 99% probability that the 90% CI of the GMR will fall completely within the interval of (0.5, 2.0).

Safety:

With 18 AD patients receiving MK-1942 + donepezil and a target rate of 80%, if the true AE rate following administration of MK-1942 + donepezil in AD patients is 60%, there is a probability of 97% that the coadministration of MK-1942 and donepezil is considered safe and tolerable (Table 11).

Table 11 Operating Characteristics for a One AE Incidence Rate

Number of Subjects Receiving MK-1942 + Donepezil	True Rate	Target Rate	Operating Characteristics “Go” means tolerable “Go” if PP (AE rate ≤ Target rate) > 60%	
			Probability of “Go”	Probability of “No Go”
18	90%	80%	10%	90%
	80%	80%	51%	49%
	70%	80%	83%	17%
	60%	80%	97%	3%
18	70%	60%	14%	86%
	60%	60%	44%	56%
	50%	60%	77%	24%
	40%	60%	95%	5%

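### Do Table 11 and the 97% overstate the reliability of the tolerability rule because its target rate comes from MK-1942-004?

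*Combined protocol and SAP*

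**What the plan says.** Sections 9.1 and 9.6.1 describe the same rule. For dizziness, nausea and emesis, and possibly other events, the analysts report the posterior probability that the incidence on MK-1942 plus donepezil is below a target. Above 60% counts as tolerable. On the target, 9.6.1 says: "The target rate is determined from the incidence of an AE associated with MK-1942 alone from MK-1942 P004, and the maximum tolerable increase". The only illustration is introduced as an example, "if the true AE rate of MK-1942 alone is 40% and the maximum tolerable increase" being 20%, which gives a target of 60%.

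Section 9.9 evaluates the rule with 18 patients on active treatment. At a target of 80% and a true rate of 60%, "there is a probability of 97% that the coadministration of MK-1942 and donepezil is considered safe and tolerable"; 9.1 repeats the figure. Table 11 has its own Target Rate column, with four true rates at a target of 80% and four at 60%.

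The PK comparison is more specific about its reference. Section 3 takes the Cmax obtained "following administration of MK-1942 to HEV from MK-1942-004, Panel C", and 9.9 uses "6 HEV receiving MK-1942 alone in MK-1942-004". The safety rule names only the study.

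**The concern.** The methods text derives the target from another study, while the sample-size section treats it as a constant. The example starts from a true rate on MK-1942 alone, which nobody will know. MK-1942-004 is small and mixed: Section 2.2.3.2 describes three panels of 8, with A and C elderly and B healthy adults, and Panel A on a different titration from B and C. Different panels could give different targets. If the target carries the sampling error of a handful of participants, the rule misclassifies more often than Table 11 shows.

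Safety is the primary objective, and Table 11 holds the only stated probabilities for it. A 97% chance of a correct call that was really nearer 80% would matter to anyone relying on the rule.

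**Working it through.** **Inputs.** n = 18 on MK-1942 plus donepezil (Table 1, Table 8); Go if the posterior probability exceeds 60% (9.6.1, Table 11); targets 80% and 60% (Table 11). The prior is not stated; uniform Beta(1,1) and Jeffreys Beta(0.5, 0.5) were both tried.

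**The plan's own figures.** With x events in 18 and a Beta(a, b) prior, Go requires P(p ≤ target) > 0.60 under Beta(a + x, b + 18 − x).

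- Target 80%, uniform prior: x = 14 gives 0.673 and x = 15 gives 0.455, so Go if x ≤ 14.
- Target 60%, uniform prior: x = 10 gives 0.667 and x = 11 gives 0.488, so Go if x ≤ 10.
- The Jeffreys prior gives the same two limits.

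P(Go) is the binomial probability of falling at or below the limit:

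| Target | True rate | Computed | Table 11 |
|---|---|---|---|
| 80% | 90 / 80 / 70 / 60% | 9.8 / 49.9 / 83.5 / 96.7% | 10 / 51 / 83 / 97% |
| 60% | 70 / 60 / 50 / 40% | 14.1 / 43.7 / 76.0 / 94.2% | 14 / 44 / 77 / 95% |

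All eight entries agree to about one point.

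**Scenario with an estimated target.** Assumptions, none of them in the plan: target = k/N + 0.20, where k of N participants on MK-1942 in MK-1942-004 had the event; uniform prior; N = 6, 12 or 18 (one, two or three panels at 6 on active each). Then P(Go) = Σ Bin(k; N, base) × P(X ≤ limit at k/N + 0.20), with X ~ Bin(18, true rate).

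For N = 6 and base 60%:

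| k | Target | Chance of k | Go if x ≤ | P(Go), true 60% | P(Go), true 90% |
|---|---|---|---|---|---|
| 0 | 20% | 0.004 | 2 | 0% | 0% |
| 1 | 36.7% | 0.037 | 5 | 0.6% | 0% |
| 2 | 53.3% | 0.138 | 9 | 26.3% | 0% |
| 3 | 70% | 0.276 | 12 | 79.1% | 0.6% |
| 4 | 86.7% | 0.311 | 15 | 99.2% | 26.6% |
| 5 or 6 | over 100% | 0.233 | 18 (always) | 100% | 100% |

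The weighted sums are 79.7% (no true increase) and 31.8% (10 points over the limit). For all three sizes:

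| Base | True increase | N = 6 / 12 / 18 | Fixed target (Table 11) |
|---|---|---|---|
| 60% | none | 79.7 / 85.2 / 88.3% | 97% |
| 60% | 30 points | 31.8 / 28.4 / 22.6% | 10% |
| 40% | none | 76.3 / 82.7 / 86.7% | 95% |
| 40% | 30 points | 31.8 / 26.7 / 24.9% | 14% |

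Exactly at the limit with base 60%, P(Go) is 49.7 / 51.6 / 48.3% against 51%. The estimated target adds noise, not a shift in one direction.

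**How far this depends on the assumed rule.** At N = 6 and base 60%, 23.3 of the 31.8 points of false Go come from targets above 100%, a value no analyst would use as a limit on a rate. Replacing k/N by (k + 1)/(N + 2) gives 95% instead of 103% at k = 5, cuts false Go to 23.8% and leaves correct Go at 79.1%. At a 6% base (emesis-like; vomiting was 3/48 over the six active panels in Table 3) with 20 points added, correct Go is 93.8 / 95.6 / 96.2% against 98% for a fixed target, a small loss. With 10 points added it is 54 / 65 / 65% against 91%. The size of the effect is set by choices the plan has not made.

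**The case for a change.** The strongest case for a change is that the rule as described is not the rule evaluated. Sections 9.1 and 9.9 give 97% as the chance of a tolerable verdict without saying that the target's own uncertainty is left out. Even if all three panels were pooled, false Go in the scenario is about twice the printed value (22.6% against 10%). Nothing in the text settles the panel before results are seen, although the PK objective does settle its own. Writing the target down would cost only a line or two.

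Part of this stands: the derivation of the target is incomplete, and one sentence in 9.9 saying that the target is taken as known would be helpful. It does not show an error. Both statements of the 97% name a target of 80%, and Table 11 displays the target for every row, so the figures are openly conditional. Once MK-1942-004 has supplied a rate and an increase has been chosen, the target is a number, and the tabulated calculation then describes the rule applied to it. Restated unconditional probabilities could not be computed until panel, N and estimator were chosen. They would still omit the difference between healthy volunteers and AD patients. Carrying the MK-1942-004 uncertainty into the rule itself is a trade-off, since no method is best across base rates.

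**Conclusion.** No change to the plan follows. Table 11 and the 97% are correct for the targets they show. What is missing is detail behind the target, which analysts can fill sensibly by setting a numeric value below 100% for each event before unblinding. The omitted prior does not matter at the two tabulated targets if it is uniform or Jeffreys.

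The apparent loss, to about 80 to 88% correct Go and 23 to 32% false Go at a 60% base, rests on an assumed uncapped plug-in rule, an assumed 20-point increase and an assumed 6 to 18 reference participants. It illustrates what a careless target could do and is not an estimate of the plan's error rates. Part of the MK-1942-004 background was not available for this review, so observed rates and numbers may be given there.

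The consequences are also limited. The posterior probabilities supplement the event counts (9.6.1), there is no primary hypothesis (9.8), escalation and stopping follow Section 6.6 and do not use this rule, and any later change to the analysis plan must be listed and explained in the study report (9.2).
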